6.14 Follow-up Telephone Contact

If subject has completed 48 Months treatment or is an Early Withdrawal from the study, there will be a FU telephone contact from the study centre to the subject approximately 30 days after their last dose of study drug. If the Early Withdrawal visit is 21 or more days after the last dose of study drug, then the FU telephone contact is not needed. The following activities will be completed:

- Review of any AEs that were ongoing at the final study centre visit or Early Withdrawal visit.
- Document result of pregnancy testing (WOCBP only).

Any clinically significant abnormalities noted at the final treatment visit should be followed up until resolved or stabilized.

The follow up phone call is not required if mavodelpar has been approved within the country and the subject switches to commercially available medication.

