The following items must be completed for subjects continuing dosing beyond Month 24:

- Provide home pregnancy testing kits for WOCBP to enable monthly pregnancy testing. Study centre will telephone the subject and remind them of the need to complete the test and confirm the test has been carried out each month. The date of test and result will be recorded in the eCRF.
- Provide a urine collection cup and instructions for collecting a second morning void for next study visit. This is provided in case the subject has their second morning void before attending the study centre at their Month 30 study visit.
- Dispense study drug and remind subject of study drug dosing requirements and study restrictions.

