Physician-PMM phenotypic description				X		X			X	X	X
Physical exam ³ (inc. weight)			X	X	X	X	X	X	X	X	X
ECG			X	X	X	X	X	X	X	X	X
Vital signs		X	X	X	X	X	X	X	X	X	X
Safety bloods haematology/biochemistry		X	X	X	X	X	X	X	X	X	X
HbA1c						X			X	X	X
Blood for bone and calcium markers				X		X		X	X	X	X
PK blood sample for REN001 ⁴		X	X	X	X	X	X	X	X	X	X
Urinalysis inc. pregnancy testing ⁵		X	X	X	X	X	X	X	X	X	X
Urine drugs of abuse		X	X	X	X	X	X	X	X	X	X
Serum FSH ⁶		X ⁷	X	X	X	X	X	X	X	X	X
Urine NTX bone markers		X	X	X	X	X	X	X	X	X	X
PROs ⁸		X	X	X	X	X	X	X	X	X	X
12MWT			X	X	X	X	X	X	X	X	X
Eye examination			X	X	X	X	X	X	X	X	X
DXA Scan ⁹									X	X	X
Dispense Study Drug			X	X		X		X	X	X	
Concomitant medication review	X										X
AE review	X										X
Dosing of study drug	X		X	X	X	X	X	X	X	X	X

¹ See Table 2. It is expected that most subjects will enrol at the STRIDE Week 24 visit with the baseline visit for this study coinciding with the STRIDE Week 24 visit. With additional assessments subjects can also enrol at the STRIDE FU visit, or at any time after exiting Study REN001-101 or STRIDE, and nDNA-PMM subjects (Table 2 and Section 6.1).

² If subject discontinues study drug, they will be required to attend an early withdrawal visit as soon as possible after their last dose of study drug. A FU telephone call by the site approx. 30 (±7) days after last dose of study drug is required unless subject transfers to commercially available mavodelpar. Clinically significant abnormalities should be followed up until resolved/stabilized.

³ Brief symptom directed physical exam can be done post baseline.

⁴ PK samples (1 or 2) will be collected at all visits except Month 3 when 4 PK samples will be collected at 0,1,2,4 hrs post dose.

⁵ Urine home pregnancy test kits will be supplied to WOCCBP to enable monthly pregnancy testing. The study centre must contact the subject to confirm the pregnancy test results. The final test will be performed prior to the follow-up telephone contact approximately 30 days after the last dose of study drug.

⁶ FSH test should be done during study if menopausal symptoms develop.

⁷ FSH to be measured for all females (aged ≥45 years) not confirmed as post-menopausal.

⁸ PROs include MFIS, PGIS and PGIC (muscle and fatigue symptoms), SF-36, PROMIS, WPAI:SHP, BPI. BPI will be carried out at Month 12 and Month 24 only. After the M24 visit, only the PGIS will be conducted at each visit. The PGIC will be carried out at Month 12, 24, 36 and 48 only.

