7.1.1.8 Collection and Reporting of AEs

7.1.1.8.1 PTE and AE Collection Periods

Collection of PTEs will commence from the time the subject signs the informed consent to participate in the study and continue until the subject is first administered study drug (Day 1) or until screen failure.

Collection of AEs will commence from the time that the subject is first administered study drug (Day 1). Routine collection of AEs will continue until the follow-up telephone contact (if required, see [Section 6.14](#)) approximately 30 days after the last study drug dose.

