7.1.1.10 Reporting Pregnancies

Although pregnancy should not be considered as an SAE *per se*, any pregnancies occurring in a study subject between baseline and the end of the contraception requirements (14 weeks after last dose for males, 30 days (approximately 1 menstrual cycle) after last dose for WOCBP) must be reported and captured as if they were SAEs.

If any subject is found to be pregnant during the study, the subject should be withdrawn, and study drug should be immediately discontinued. In addition, any pregnancies in the partner of a male subject during the study or for 14 weeks after the last dose of study drug should also be recorded following authorisation from the subject's partner.

All reported pregnancies will be followed up to final outcome, using the paper pregnancy follow-up form. The outcome, including any premature termination, must be reported to the Sponsor. An evaluation after the birth of the child will also be conducted.

Reports should be sent within 24 hours using the Pregnancy Report Form. If the female subject and/or female partner of a male subject agrees to the primary care physician being informed, the Investigator should notify the primary care physician that the subject/female partner of the subject was participating in a clinical study at the time she became pregnant and provide details of treatments the subject received.

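### The final follow-up call lists review of ongoing AEs only, although AE and SAE collection runs to about 30 days after the last dose; the call waiver and the final pregnancy kit also need reconciling with Table 3

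*Protocol*

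**What the plan says.** **The final call.** Section 6.14 states that "there will be a FU telephone contact from the study centre to the subject approximately 30 days after their last dose of study drug". It lists two tasks: "Review of any AEs that were ongoing at the final study centre visit or Early Withdrawal visit", and recording the pregnancy test result for women of childbearing potential (WOCBP). By contrast, the Month 24, Month 48 and Early Withdrawal visits (6.9, 6.13) list a review of AEs with no such restriction.

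**The collection windows.** Section 7.1.1.8.1 says "Routine collection of AEs will continue until the follow-up telephone contact", at about 30 days after the last dose, and adds that the call may not be required, with a reference to 6.14. Section 7.1.1.9 requires every SAE to about 30 days after the last dose and does not tie this to the call. Section 7.1.1.5 has AESIs reported in the same way as SAEs.

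**The waiver.** Section 6.14 drops the call "If the Early Withdrawal visit is 21 or more days after the last dose of study drug", and also when the subject moves to commercial drug. Table 3 footnote 2 says "A FU telephone call by the site approx. 30 (±7) days after last dose of study drug is required unless subject transfers to commercially available" drug. It names no Day 21 exception. The SAP repeats that footnote in Section 3.4.

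**The final pregnancy test.** Table 3 footnote 5 says "The final test will be performed prior to the follow-up telephone contact approximately 30 days after the last dose of study drug". Section 6.13 lists a kit for that test. In Section 6.9, which also governs withdrawal before Month 24, kits appear only under the line "The following items must be completed for subjects continuing dosing beyond Month 24".

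**Partner pregnancies.** Section 7.1.1.10 asks for a record of "any pregnancies in the partner of a male subject during the study or for 14 weeks after the last dose of study drug".

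**The concern.** The primary endpoints are counts of AEs, SAEs, AESIs, AEs leading to discontinuation and AEs leading to death (Protocol 3.2.1). The protocol defines a treatment-emergent AE by its onset or worsening after the first dose and gives no end point (7.1.1.1). SAP Section 12.1 likewise treats an AE as emergent unless it clearly precedes dosing, and its last reporting period, after Day 336, is open-ended. The SAP's limit of last dose plus one day (Section 8.2) applies to measurements, not to AEs. An event starting two weeks after the last capsule is therefore inside the primary count.

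A site that follows the 6.14 list literally will ask about old events and not about new ones. New post-dose events would then enter the database mainly when the subject volunteers them. The same list-following problem affects the final pregnancy kit. The waiver leaves sites with two different instructions on whether a call is due.

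**Working it through.** No test, power or sample size calculation is involved. The check is day arithmetic on the protocol's own windows, followed by a side-by-side reading.

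**Inputs**
- Call: about Day 30 after the last dose (6.14), window ±7 days (Table 3 footnote 2).
- Waiver: Early Withdrawal visit on Day 21 or later (6.14).
- Partner-pregnancy window: 14 weeks (7.1.1.10).

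**1. Interval with no listed prompt for new AEs**
- Permitted call days: 30 − 7 = 23 to 30 + 7 = 37.
- Completers, assuming the Month 48 visit falls at about the last dose: 23 to 37 days, nominally 30.
- Early Withdrawal visit on Day 0: 30 − 0 = 30 days nominally. On Day 20: 30 − 20 = 10 days.

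**2. Do other sections supply the prompt?**
- Section 7.1.1.8.2 provides a neutral question about AEs, but ties it to study visits. Otherwise it says that subjects may report events, which is spontaneous reporting.
- Section 7.1.1.11 follows events already experienced until they resolve.
- Section 7.1.1.4 makes a worsening a new AE. A review of ongoing AEs would catch that, so the gap concerns events with no earlier record.

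**3. Day 21 waiver**
- Against Day 30: 30 − 21 = 9 days at most, and zero once the visit is on Day 30 or later. Only visits on Days 21 to 29 fall short.
- Against the earliest permitted call: 23 − 21 = 2 days.

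**4. Final kit**

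| Source | Withdrawal before Month 24 | Month 48 or later withdrawal |
|---|---|---|
| Visit list | 6.9: kit only if dosing continues | 6.13: final kit listed |
| Table 3 footnote 5 | final test expected | final test expected |
| 6.14 | result recorded | result recorded |

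The visit list for withdrawal before Month 24 is the one that does not match.

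**5. Partner-pregnancy window**
- 14 × 7 = 98 days.
- After a call on Day 37: 98 − 37 = 61 days. After a call on Day 23: 98 − 23 = 75 days. That is 62% to 77% of the window.
- If a Day 21 visit is the last contact: 98 − 21 = 77 days (79%).

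**The case against.** The best defence is that 7.1.1.8.1, not 6.14, governs AE collection. It keeps routine collection running to the call without restricting it to ongoing events, 7.1.1.9 does the same for SAEs, and a trained site would ask about both. This stands in part: the documents conflict, and lost data are not demonstrated. It does not remove the point, because 6.14 is the list a site works from during the call and it is narrower than the sections it serves.

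A reader might infer four stronger things, and the documents do not support them.

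- *That follow-up ends before the AE collection window.* For routine AEs, 7.1.1.8.1 defines the end of collection by the call and acknowledges that the call may not be required. For completers the fault is the content of the call, not its timing.
- *That the waiver leaves early withdrawals poorly covered.* It replaces a telephone call with an in-person visit on Day 21 or later, with unrestricted AE review, laboratory tests, ECG and a pregnancy test. Such late visits should be uncommon, since 6.9 and 6.13 ask for the visit as soon as possible after the last dose. What remains is the mismatch with footnote 2.
- *That women who withdraw before Month 24 get no final test.* Footnote 5 supplies kits to WOCBP generally, Section 1.4.2.4 asks for monthly tests until study completion, a woman who stops between visits may hold unused kits, and 6.9 includes a test at the visit. This is an omitted line, not a denial of testing.
- *That partner pregnancies would be missed and a 14-week call is needed.* Section 7.1.1.10 is a duty to report, promises no contact at Day 98, and concerns something that is not a study endpoint. Since 4.6 ends the study at the last follow-up call, an added call could also delay completion by about 98 − 30 = 68 days.

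**Conclusion.** The point holds for the content of the final call. As written, 6.14 gives no prompt for new-onset AEs over about 23 to 37 days for completers and nominally 10 to 30 days for Early Withdrawal visits before Day 21, although those events belong to the primary endpoints. This assumes that sites follow the 6.14 list literally and that a completer's last visit falls near the last dose. The number of events affected cannot be estimated from the documents.

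Two lesser inconsistencies are also real: the waiver against Table 3 footnote 2 (at most 9 days, or 2 against the earliest permitted call), and the 6.9 kit list against footnote 5 and 6.14. The partner-pregnancy window is worth noting only. It has no scheduled contact for 61 to 75 of its 98 days, or 77 if the call is waived at Day 21, and it relies on spontaneous reporting over that time.

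**What to change.** 1. Change the AE bullet in 6.14 to: *Review of ongoing AEs and any new AEs, SAEs or AESIs since the last visit.* The cost is one line of protocol text and one more question in a call that is already scheduled.
2. Reconcile the Day 21 waiver in 6.14 with Table 3 footnote 2, and with its copy in SAP Section 3.4, so that all three give the same conditions for omitting the call. Keeping the waiver costs footnote text only. Removing it adds one call for each subject whose withdrawal visit is on Day 21 or later.
3. In 6.9, list the final home pregnancy kit for WOCBP at Early Withdrawal before Month 24, as 6.13 already does for later withdrawals. The cost is at most one kit per woman concerned.

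No change is asked for on partner pregnancies. None of these edits affects the sample size or the planned summaries.

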6.15 Unscheduled Visits

Unscheduled visits may also be arranged at any time at the discretion of the investigator as clinically indicated. These visits should be recorded on the unscheduled study visit pages in the electronic Case Report Form (eCRF).

Table 2: Screening and Baseline Visits

Assessments	Option 1 Enrolment at STRIDE Week 24 ¹	Option 2 Enrolment at STRIDE FU ²	Option 3 mtDNA-PMM subjects from REN001-101 or after exiting STRIDE ³		Option 4 nDNA-PMM subjects ³	
	Baseline	Baseline	Screening	Baseline	Screening	Baseline
Informed Consent	X	X	X		X	
Demography	STRIDE Baseline	STRIDE Baseline	X		X	
Medical History	STRIDE Baseline	STRIDE Baseline	X		X	
Physician completion of PMM Phenotype	STRIDE Week 24	X		X		X
Physical Exam (inc weight and height) ⁴	STRIDE Week 24	X	X	X	X	X
ECG	STRIDE Week 24	X	X	X	X	X
Vital signs	STRIDE Week 24	STRIDE FU	X	X	X	X
Safety labs	STRIDE Week 24	X	X	X	X	X
HbA1c ⁵	STRIDE Week 24	X	X	X	X	X
HEP B/C/HIV ⁶			X		X	
Blood for bone and calcium markers	STRIDE Week 24	X		X		X
PK blood sample for REN001	STRIDE Week 24 ⁷	X		X		X
Urinalysis, inc pregnancy testing ⁸	STRIDE Week 24	STRIDE FU		X		X
Serum pregnancy testing			X		X	
Urine drugs of abuse ⁹	STRIDE Week 24	X	X	X	X	X
Serum FSH		X ¹⁰	X		X	
Urine NTX bone markers	STRIDE Week 24	X		X		X
PROs	STRIDE Week 24	X		X		X
12MWT	STRIDE Week 24	X		X		X ¹¹

¹ Most of baseline data will be STRIDE Week 24 data. Additional assessments to be carried out on the same day (Section 6.1.1).

² Baseline tests to be carried out at the STRIDE FU visit.

³ Separate screening and baseline visits required (Section 6.1.3). nDNA subjects will not be recruited in France.

⁴ Height only collected at screening/baseline visits

⁵ Subjects enrolling in Germany require a HbA1c to be performed 8 weeks prior to baseline. For subjects enrolling at STRIDE Week 24 or FU these samples could coincide with STRIDE Week 18 or 24 visits respectively. Informed consent must be obtained prior to these samples being taken.

⁶ Subjects enrolling in Germany require a Hepatitis B/C/HIV to be performed 8 weeks prior to baseline. For subjects enrolling at STRIDE Week 24 or FU these samples could coincide with STRIDE Week 18 or 24 visits respectively. Informed consent must be obtained prior to these samples being taken.

⁷ Data will only be reported in the REN001-201 CSR

⁸ Urine pregnancy testing will be carried out at all visits, excluding the option 3 & option 4 screening visit which will be a serum pregnancy test. Women aged ≥45 years will receive a urine pregnancy test at the STRIDE Week 24 visit in lieu of an FSH test which will be conducted at Month 1, if required.

⁹ Subject will be excluded at the Investigator's discretion for alcohol/drug dependency. Use for medical reason is acceptable with prescription evidence.

¹⁰ FSH for females aged ≥45 years not confirmed as post-menopausal in the STRIDE study (FSH not conducted at STRIDE Week 24 visit, see footnote 5).

¹¹ There must be a minimum of 4 weeks between the screening and baseline 12MWT.

	STRIDE Week 24	STRIDE Week 24	STRIDE Week 24	X ¹	X ¹
Eye examination					X ¹
Wrist radiograph ²					X
DXA Scan ³	STRIDE Week 24	STRIDE Week 24	STRIDE Week 24	STRIDE Week 24	X
Concomitant Medication review	STRIDE Week 24	STRIDE FU	STRIDE FU	X	X
AE Review ⁴	STRIDE Week 24	STRIDE FU	STRIDE FU	X	X
Dispense Study Drug	X	X	X	X	X
First dose of study drug ⁵	X	X	X	X	X

¹ Eye examination can be done at any time between the screening and baseline visit for scheduling reasons.

² Subjects <25 years old.

³ Optional. Only conducted at sites which participated in the DXA sub-study. If a DXA scan was performed at STRIDE Week 24 it will be regarded as the baseline. Sites with approvals in place should review all subjects against the additional protocol criteria (Section 4.3) and perform DXA if subject eligible and not performed in STRIDE.

⁴ Review of pre-treatment events for subjects enrolling at option 3 and option 4: after exiting STRIDE or REN001-101, and nDNA-PMM subjects.

⁵ Subject enrolling at STRIDE Week 24 should take the first dose the day after the Baseline visit, this will be confirmed with a telephone call from site the next day. Subject enrolling at STRIDE FU or after exiting STRIDE or Study REN001-101, and nDNA-PMM subjects should take the first dose at the study centre baseline visit.

Table 3: Schedule of Activities

Assessments/Time*	Screening / Baseline Visits ¹	Month 1 (Day 28)	Month 3 (Day 84)	Month 6 (Day 168)	Month 9 (Day 252) Germany only	Month 12 (Day 336)	Month 15 (Day 420) Germany only	Month 18 (Day 504)	Month 24 (Day 672) or pre M24 Early Withdrawal ²	Month 30 (Day 840), M36 (Day 1008), M42 (Day 1176)	Month 48 (Day 1344) or post M24 Early Withdrawal ²
Window for visit		±3 days	±7 days	±7 days	±21 days	±21 days	±21 days	±21 days	±21 days	±21 days	±21 days
Physician-PMM phenotypic description				X		X			X	X	X
Physical exam ³ (inc. weight)			X	X	X	X	X	X	X	X	X
ECG			X	X	X	X	X	X	X	X	X
Vital signs		X	X	X	X	X	X	X	X	X	X
Safety bloods haematology/biochemistry		X	X	X	X	X	X	X	X	X	X
HbA1c						X			X	X	X
Blood for bone and calcium markers				X		X		X	X	X	X
PK blood sample for REN001 ⁴		X	X	X	X	X	X	X	X	X	X
Urinalysis inc. pregnancy testing ⁵		X	X	X	X	X	X	X	X	X	X
Urine drugs of abuse		X	X	X	X	X	X	X	X	X	X
Serum FSH ⁶		X ⁷	X	X	X	X	X	X	X	X	X
Urine NTX bone markers		X	X	X	X	X	X	X	X	X	X
PROs ⁸		X	X	X	X	X	X	X	X	X	X
12MWT			X	X	X	X	X	X	X	X	X
Eye examination			X	X	X	X	X	X	X	X	X
DXA Scan ⁹									X	X	X
Dispense Study Drug			X	X		X		X	X	X	
Concomitant medication review	X										X
AE review	X										X
Dosing of study drug	X		X	X	X	X	X	X	X	X	X

¹ See Table 2. It is expected that most subjects will enrol at the STRIDE Week 24 visit with the baseline visit for this study coinciding with the STRIDE Week 24 visit. With additional assessments subjects can also enrol at the STRIDE FU visit, or at any time after exiting Study REN001-101 or STRIDE, and nDNA-PMM subjects (Table 2 and Section 6.1).

² If subject discontinues study drug, they will be required to attend an early withdrawal visit as soon as possible after their last dose of study drug. A FU telephone call by the site approx. 30 (±7) days after last dose of study drug is required unless subject transfers to commercially available mavodelpar. Clinically significant abnormalities should be followed up until resolved/stabilized.

³ Brief symptom directed physical exam can be done post baseline.

⁴ PK samples (1 or 2) will be collected at all visits except Month 3 when 4 PK samples will be collected at 0,1,2,4 hrs post dose.

⁵ Urine home pregnancy test kits will be supplied to WOCCBP to enable monthly pregnancy testing. The study centre must contact the subject to confirm the pregnancy test results. The final test will be performed prior to the follow-up telephone contact approximately 30 days after the last dose of study drug.

⁶ FSH test should be done during study if menopausal symptoms develop.

⁷ FSH to be measured for all females (aged ≥45 years) not confirmed as post-menopausal.

⁸ PROs include MFIS, PGIS and PGIC (muscle and fatigue symptoms), SF-36, PROMIS, WPAI:SHP, BPI. BPI will be carried out at Month 12 and Month 24 only. After the M24 visit, only the PGIS will be conducted at each visit. The PGIC will be carried out at Month 12, 24, 36 and 48 only.

⁹ Optional DXA scan will only be conducted at sites which participated in the DXA sub-study. Eligible subjects must have had a DXA scan at baseline.

*Additional unscheduled visits may be arranged at any time at the discretion of the investigator as clinically required.

7 PARAMETERS AND METHODS OF ASSESSMENT

7.1 Safety Parameters

7.1.1 Adverse Events

7.1.1.1 Definitions

Pre-treatment Event (PTE):

A PTE is defined as any untoward medical occurrence in a clinical investigation subject who has signed informed consent to participate in a study but prior to administration of any study drug; it does not necessarily have to have a causal relationship with study participation. Hence, occurrences between the screening and baseline visits for those mtDNA-PMM subjects enrolling from REN001-101 (UK only), or after exiting the STRIDE study, and nDNA-PMM subjects will be reported as PTEs. For those mtDNA-PMM subjects who transition to this study immediately from STRIDE, only ongoing adverse events at the time of enrolling in this study will be reported as a PTE (see Section 7.1.1.3).

Adverse Event (AE):

- An AE is any untoward medical event that occurs in a subject who has received study drug and does not necessarily have a causal relationship with study treatment. An AE can therefore be any unfavourable and unintended sign (including an abnormal laboratory finding), symptom, or disease temporally associated with the use of an investigational product, whether or not related to the product.
- A TEAE will be defined as an AE that begins or that worsens in severity after the first dose of study drug has been administered.
- An adverse drug reaction (ADR) is any untoward and unintended response in a subject to an investigational medicinal product which is related to any dose administered to that subject.
- An unexpected adverse reaction is an adverse reaction the nature and severity of which is not consistent with the information about the medicinal product in the Investigator's Brochure.

All PTEs/AEs, including intercurrent illnesses, occurring during the study will be documented in the eCRF.

Each event should be recorded to represent a single diagnosis. Accompanying signs (including abnormal laboratory values or ECG findings) or symptoms should NOT be recorded as additional AEs. If a diagnosis is unknown, sign(s) or symptom(s) should be recorded appropriately as an AE(s).

